17.8 Statistical Analysis

17.8.1 General Considerations

Statistical analyses will be performed using SAS® v9.4 or higher (SAS Institute, Cary NC, USA).

Baseline demographic and other baseline characteristics, together with safety analyses will be performed on all enrolled subjects. Baseline values are defined as the last valid value prior to treatment.

All statistical tests will be two-sided. If statistical tests are performed nominal p-values will be presented. Where confidence limits are appropriate, a two-sided 95% confidence interval will be constructed.

For comparison of means (continuous variables), the two-sample t-test or the Wilcoxon rank sum test will be used as appropriate. For comparison of proportions (categorical variables), the Chi-squared test or Fisher's exact test will be used as appropriate.

17.8.2 Significance levels and handling of type I error

17.8.2.1 Type I Error

The overall significance level for this study is 5% using two-tailed tests and two sided Confidence Intervals (CI).

The analyses of this study are mainly descriptive in nature.

17.8.3 Demographic and Other Baseline Variables

Demographic and baseline condition related characteristics will be tabulated. Continuous variables will be summarized by a mean, standard deviation, minimum, median and maximum, and categorical variables by a count and percentage.

17.8.4 Disposition of Subjects

Treatment tolerability will be presented, the number and percent of subjects who fail to complete the study and the number and percent of subjects who fail to complete the study because of Adverse Events will be presented. Time to withdrawal will also be assessed and presented by Kaplan-Meier.

17.8.5 Efficacy Analysis

The subject's success status (i.e. if the subjects achieve an increase from baseline of at least 1 weekly SBM during at least 3 out of the 6 treatment weeks) will be calculated. The success rate will be presented along with its exact binomial two sided 95% Confidence Intervals (CI).

Ease of Use will be presented in a tabular form.

Doc No: 220CLD

Rev: 03 Date: August 26, 2016

Page 58 of 93

The CSBM success rate will be analyzed in the same manner.

The change from baseline in number of weekly SBM will be modeled with an Analysis of Covariance (ANCOVA) model, with baseline weekly number of SBM and site as covariates. The adjusted means of the change from baseline will be presented along with its 95% CI.

The change from baseline in count of weekly CSBM, and in symptoms, will be analyzed with similar ANCOVA models, with their respective baseline values as covariate.

Time to occurrence of SBM after intake of the first Vibrant capsule will be assessed and presented by Kaplan-Meier curves.

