17.4 Sample size

The chosen sample size is 120 subjects who will be enrolled and complete the 6 treatment weeks.

The final sample size will be determined following the completion of the interim analysis, based on the efficacy of the new frequency of vibration capsule.

The sample size account for a potential 10% of drop-outs.

The sample size will be increased to at least 134 to account for a potential 10% of dropouts, as needed.

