17.5 Randomization

This is an open-label, single-arm study.

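### In this single-arm study the ANCOVA 95% CI for mean change leaves out the sampling variation of baseline, so it under-covers the population mean change, materially for symptoms and slightly for weekly SBM

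*Combined protocol and SAP*

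**What the plan says.** Section 17.5 is plain about the design: "This is an open-label, single-arm study". Section 17.8.5 nevertheless models the change in weekly SBM by ANCOVA, "with baseline weekly number of SBM and site as covariates", and says "The adjusted means of the change from baseline will be presented along with its 95% CI". The changes in weekly CSBM and in symptoms "will be analyzed with similar ANCOVA models, with their respective baseline values as covariate"; a site term for these is implied only by the word similar.

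Section 17.8.1 adds the general rule: "Where confidence limits are appropriate, a two-sided 95% confidence interval will be constructed". Section 17.8.2.1 sets a two-sided 5% level but describes the analyses as mainly descriptive.

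The plan does not state the baseline value at which the mean is adjusted, how sites are weighted in it, or whether the interval is meant to be conditional on the observed baselines. It specifies no other interval for a mean change; the mean comparisons named in 17.8.1 are two-sample tests, which do not fit a one-arm study.

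**The concern.** Baseline adjustment earns its place in a randomised comparison. There the chance variation in who was sampled is shared by the arms and cancels from the difference, leaving the residual variance as the right yardstick. With one arm nothing cancels. The change depends on baseline, and a new sample would have a different mean baseline and so a different mean change. The ANCOVA standard error treats the observed mean baseline as fixed and ignores that source of variation.

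Section 17.2.2 lists nine change-from-baseline endpoints: SBM, CSBM, stool consistency, bloating, gas, abdominal pain, straining, discomfort, and pain during defecation. Their intervals would be labelled 95% but would cover the population mean change less often. In an uncontrolled study with no formal test of the primary endpoint, intervals are a main expression of uncertainty about these outcomes.

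**Working it through.** **Inputs from the plan.** One arm; two-sided 95% CI; 120 completers (17.4: "The chosen sample size is 120 subjects who will be enrolled and complete the 6 treatment weeks"); up to 15 centers (15.1), so 8 completers per site on average; run-in SBM from 1 to below 3 per week (15.9). The plan's own figure reproduces: 120/0.9 = 133.3, hence 134. That confirms n = 120 but does not bear on interval width. The plan gives no SD of change, correlation, or target precision, so those below are assumptions.

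**Formula.** Write change = a + b × baseline + e. With no site term, the adjusted mean at the sample-mean baseline is exactly the raw mean change.

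- ANCOVA variance used: Var(e)/n
- True sampling variance: Var(e)/n + b² × Var(baseline)/n = Var(change)/n
- Ratio of standard errors: √(1 − q²), where q is the correlation of change with baseline
- Approximate coverage: 2Φ(1.98 × ratio) − 1

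**Symptom-type outcomes.** Assume equal SDs in run-in and treatment (set to 1) and correlation r between them. Then b = r − 1, Var(e) = 1 − r², Var(change) = 2(1 − r), and the ratio is √((1 + r)/2).

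| r | Ratio | Approximate coverage |
|---|---|---|
| 0.3 | √0.65 = 0.81 | 89% |
| 0.5 | √0.75 = 0.87 | 91% |
| 0.7 | √0.85 = 0.92 | 93% |

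Simulation at n = 120 agrees: 88.0/91.6/92.8% for the baseline-only model, against about 95% for the one-sample t interval. At r = 0.5 the half-widths are 1.98/√120 = 0.181 SD of change (correct) and 0.181 × 0.866 = 0.157 (ANCOVA). The same ratios hold with a site term if sites are equal in size or weighted by size.

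**Equal site weights.** If each site counts equally and baseline is held at the overall sample mean, the adjusted mean is a + b × (sample-mean baseline) + the average of the site-mean residuals. The omitted term is still b² × Var(baseline)/n, but the residual part grows by f², where f depends on the spread of site sizes. For simulated site sizes from 25 down to 1, f = 1.54. At r = 0.5:

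- Model SE: √(0.75/120) × 1.54 = 0.122
- Omitted variance: 0.25/120 = 0.0021
- True SE: √(0.122² + 0.0021) = 0.130
- Raw-mean SE: √(1/120) = 0.091

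The interval is therefore 0.122/0.091 = 1.33 times the raw-mean width, yet the ratio to its own true error is 0.94 and coverage is 93.6%, which the simulation reproduces. The formula gives 92.6% at r = 0.3 (simulated 91.9%) and 94.4% at r = 0.7. Under milder imbalance (f = 1.089) it gives 0.88/0.94/1.00 of the raw-mean width and coverage of about 90/92/93.5% for r = 0.3/0.5/0.7.

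**Weekly SBM.** I take baseline as the run-in average used for eligibility. With a full 14-day diary the possible values are 1, 1.5, 2 and 2.5, so the SD is 0.56 if they are evenly spread and at most 0.75. Coverage below is for the baseline-only model.

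| Baseline SD | Treatment SD | r | Ratio | Approximate coverage |
|---|---|---|---|---|
| 0.56 | 2.0 | 0.3 | 1.00 | 95% |
| 0.56 | 1.5 | 0 | 0.94 | 93.6% |
| 0.40 | 2.5 | 0.5 | 0.93 | 93.5% |
| 0.75 | 1.0 | 0 | 0.80 | 89% (extreme) |

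Over baseline SD 0.40–0.56, treatment SD 1.5–2.5 and r 0–0.5, coverage is about 93.5–95%.

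**CSBM.** As a subset of SBM it lies between 0 and below 3 at baseline, but no SD can be derived, so the size is unknown.

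**The case against.** The strongest reply is that a regression interval is properly read as conditional on the observed baselines, and on that reading it is valid. The defect would then be an unstated estimand. This is technically right, and the plan does not exclude it. But the stated objective is the efficacy of the new capsule frequency in patients with Functional Constipation (sections 12 and 17.1), and a reader will take the interval as a statement about such patients.

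Second, the planned SBM model includes site. A reader might infer from the baseline-only algebra that every interval is too narrow, by the factor √((1 + r)/2). The documents do not support that, because site weighting is unstated and equal weights with unequal sites can make the interval wider than the raw-mean one. A reader might also infer that the baseline covariate buys no precision at all. That is exact only without site, with equal-sized sites, or with size weights. With equal weights and very unequal sites it lowers the simulated SD of the estimate from 0.139 to 0.130 at r = 0.5, though the raw mean, at 0.091, is still more precise. Both corrections stand; the under-coverage remains.

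Third, the consequence is modest. These are secondary, mainly descriptive outcomes. At r = 0.5 the gap in half-width is 0.181 − 0.157 = 0.024 SD of change. The synopsis promises means and SDs for continuous variables; if that extends to change scores, a reader could form the correct interval. It would therefore be too much to call the ANCOVA intervals the whole basis for a claim of improvement. Neither interval addresses placebo response or regression to the mean. All of this limits severity, but not the case for an inexpensive correction.

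**Conclusion.** The point holds as a recommended correction, not as a threat to the main result. Evaluated at the sample-mean baseline, the ANCOVA interval omits slope² × Var(baseline)/n and understates the sampling error of the adjusted mean as an estimate of the population mean change.

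- **Symptom-type outcomes:** coverage is about 88–93% under equal SDs and correlation 0.3–0.7 when there is no site term, or sites are equal in size or size-weighted.
- **Equal site weights, very unequal sites:** coverage is about 92–95%, with an estimate less precise than the raw mean. Under milder imbalance the shortfall lies between these cases.
- **Weekly SBM:** about 93–95% over most plausible values. The SBM sentence is the one that promises the interval, and there the effect is small, so SBM and symptoms should not be put on the same footing.
- **CSBM:** size unknown.

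The algebra is firm; the sizes rest on assumed SDs and correlations. The exact binomial intervals for the primary SBM success rate and for the CSBM success rate are unaffected.

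**What to change.** In section 17.8.5, make the mean within-subject change with a one-sample (paired) t 95% CI, or a bootstrap over subjects, the reported interval for every change-from-baseline endpoint. In simulation the t interval covered 94.4–95.4% in every scenario examined. Keep the ANCOVA only to describe how change depends on baseline and site. If adjusted means are still shown, state the baseline value used and the site weighting.

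The cost is one or two sentences and no extra data. For symptom-type outcomes intervals would be about 8–24% wider (1/0.922 = 1.08; 1/0.806 = 1.24) relative to a baseline-only or size-weighted ANCOVA. They may be narrower if sites would have been weighted equally.

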15.10 Rescue Treatment

Patients with no spontaneous bowel movement for 3 consecutive days will be authorized to use rescue, if they wish to. The patients will not be required to contact the investigator prior to taking any medication/supplement but they will be required to declare the rescue medication on their eDiary. The following treatment is recommended (not by order):

- 1. Dulcolax® suppository/bisacodyl suppository
- 2. Fleet Enema®
- 3. Dulcolax®/bisacodyl tablet (1x5mg)

If the patient takes a rescue medication/supplement that is not in the above list, the patient will need to give a reason for it in his eDiary.

If the investigator prescribes a rescue medication/supplement that is not in the above list, the investigator will need to mention it and give the reason in a note to file or appropriate form.

Doc No: 220CLD

Rev: 03 Date: August 26, 2016

Page 47 of 93

Patients who take rescue medication three times or more during the run-in period will be considered as screening failures.

A spontaneous bowel movement is defined as a bowel movement that occurs at least 24h after laxative/rescue intake and without digital maneuver.

A complete spontaneous bowel movement is defined as a spontaneous bowel movement associated with a feeling of complete evacuation by the patient.

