17.2.2 Secondary Efficacy Endpoints

Secondary efficacy endpoints include:

- Ease of use
- CSBM success rate, defined as as an increase from the run-in period of at least one weekly Complete Spontaneous Bowel Movement (CSBM) during at least 3 of the 6 weeks of treatment. Subjects with less than 2 weeks (with at least 5 days per week) of valid diary during the treatment period will be considered as non-evaluable.
- Change from baseline in weekly number of Spontaneous Bowel Movement (SBM).
- Change from baseline in weekly number of Complete Spontaneous Bowel Movement (CSBM).
- Change from baseline in average stool consistency, using the Bristol Stool Scale
- Change from baseline in average bloating.
- Change from baseline in average abdominal gas.
- Change from baseline in average abdominal pain.
- Change from baseline in average straining.
- Change from baseline in abdominal discomfort.
- Change from baseline in average abdominal pain during defecation.
- Time to occurrence of spontaneous bowel movement after capsule.

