17.8.8 Handling of Missing Data

Missing value will not be imputed and will be left "as-is". For the time to first SBM analysis, subjects with no known SBM will be considered left censored.

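### The time-to-first-SBM analysis has no rule for rescue taken before the first SBM, beyond the 24 h exclusion in the SBM definition, so one curve pools aided and unaided SBMs

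*Combined protocol and SAP*

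**What the plan says.** Section 17.2.2 lists the endpoint as "Time to occurrence of spontaneous bowel movement after capsule". Section 17.8.5 fixes the origin, event and method: "Time to occurrence of SBM after intake of the first Vibrant capsule will be assessed and presented by Kaplan-Meier curves". Section 17.8.8 adds the only other rule: "For the time to first SBM analysis, subjects with no known SBM will be considered left censored". None of the three mentions rescue.

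Rescue enters through section 15.10. It is optional: "Patients with no spontaneous bowel movement for 3 consecutive days will be authorized to use rescue, if they wish to". No prior call is needed ("The patients will not be required to contact the investigator prior to taking any medication/supplement"), but use must be declared in the eDiary. The same section defines the event: "A spontaneous bowel movement is defined as a bowel movement that occurs at least 24h after laxative/rescue intake and without digital maneuver".

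**The concern.** The plan does not treat rescue between the first capsule and the first SBM as a competing event or a censoring time, and it sets no sensitivity analysis for it. The 24 h exclusion removes the movement that the rescue produces at once. The next movement after that window is an SBM by definition and closes the subject's time.

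Take two subjects dosed on day 0. One has an unaided SBM on day 5. The other uses an enema on day 4 and has a countable SBM on day 6. Both enter the curve as events, at 5 and 6 days, and nothing marks the second as having needed rescue.

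The single curve therefore answers how soon an SBM occurred, whether or not rescue came first. The endpoint's wording invites a reader to take it as an SBM that followed the capsule alone. With one arm and no control curve, the report would not show how many subjects had an SBM without laxative help.

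**Working it through.** The documents give no figure for this endpoint. The one design figure that can be checked is the enrolment target in section 17.4: 120 / 0.9 = 133.3, rounded up to 134, which agrees. The 120 completers are used below only to turn shares into counts.

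**Inputs from the documents**
- Rescue is authorised after 3 consecutive days without an SBM (15.10): 3 × 24 = 72 h if a day is 24 h.
- A movement counts only if it is at least 24 h after rescue (15.10). The earliest countable SBM after a rescue at 72 h is thus at 72 + 24 = 96 h.
- Run-in average of at least 1 and fewer than 3 SBM per week (15.9). The value 3 is the open upper bound.

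**Assumptions, not in the documents**
- SBMs follow a Poisson process at rate r per week, with no device effect.
- The three-day clock starts at the first capsule.
- From day 3, a subject still without an SBM takes rescue on any given day with probability q. Rescue may repeat, and it has no effect beyond 24 h.

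**Step 1: who may take rescue.** The share still at risk after t days is S(t) = exp(−r·t/7).

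| r per week | S at 72 h | of 120 | S at 96 h | of 120 |
|---|---|---|---|---|
| 1 | 65% | 78 | 56% | 68 |
| 2 | 42% | 51 | 32% | 38 |
| 3 | 28% | 33 | 18% | 22 |

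These are the shares allowed rescue, not the shares taking it. If the three days began before the capsule, rescue is permitted earlier than 72 h. If days are counted by calendar, it could be permitted as late as about 96 h.

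**Step 2: the two quantities at day 14.** Eleven daily steps run from day 3 to day 14. Write a = (1−q)(1−exp(−r/7)) and b = (1−q)·exp(−r/7).
- No rescue at all: 1 − exp(−2r).
- Planned curve: 1 − S(3)·(1−a)^11.
- SBM before any rescue: 1 − S(3) + S(3)·a·(1−b^11)/(1−b).
- Rescue before SBM: S(3)·q·(1−b^11)/(1−b).

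For r = 2 and q = 0.25, S(3) = 0.4244, a = 0.1864 and b = 0.5636. The planned curve is 1 − 0.4244 × 0.8136^11 = 0.956. SBM before rescue is 0.5756 + 0.4244 × 0.1864 × 2.287 = 0.757.

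| r | q | No rescue | Planned curve | SBM before rescue | Rescue before SBM |
|---|---|---|---|---|---|
| 1 | 0.25 | 86.5% | 79.5% | 53.3% | 46.1% |
| 1 | 0.50 | 86.5% | 69.5% | 42.5% | 57.5% |
| 2 | 0.25 | 98.2% | 95.6% | 75.7% | 24.3% |
| 2 | 0.50 | 98.2% | 90.1% | 66.0% | 34.0% |

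**Step 3: the direction.** In every row the planned curve lies below the no-rescue value, because the 24 h exclusion delays countable events. A laxative effect lasting beyond 24 h would act the other way, and the documents give no figure for one.

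**Step 4: the median.** Without rescue it is 7·ln 2 / r days: 2.43 at r = 2 and 1.62 at r = 3. Both fall before day 3, so with the clock started at the capsule rescue cannot move them. At r = 1 the median is 4.85 days, inside rescue-permitted time. In a simpler simulation with at most one rescue per subject, taken as soon as it was allowed by 25% of those eligible, the r = 1 median rose from about 116 h to 123 h. When the clock ran from the last SBM before the capsule, the r = 2 median rose from about 58 h to 64 h. It was never shorter.

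**The case against.** The other side has four fair points.

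- **The analysis is not blind to rescue.** The SBM definition builds in the 24 h exclusion. A reader might say that the plan ignores rescue; section 15.10 shows that it does not. What is missing is a rule for what follows the 24 h window.
- **No inflation is shown.** A reader might infer from 96% against 76% that the planned curve is inflated. It is not: 96% is below the 98% that the same model gives with no rescue. Counting any SBM that meets the definition is a legitimate treatment-policy reading.
- **The later SBM cannot be assigned to the rescue.** A reader might say that a day-6 SBM after a day-4 enema measures the enema. The documents do not support that: on the two-days-on, one-day-off schedule the subject would have taken further capsules by then. Equally, a single-arm curve does not isolate the capsule's effect for a subject who took no rescue.
- **Uptake is assumed.** Rescue is optional, and subjects with three or more uses in the run-in are screening failures, which makes heavy uptake less plausible. At rates near 3 per week, fewer than a third of subjects reach 72 h without an SBM.

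All four stand, and they limit the point. They do not remove it: the plan does not state which reading it intends, and the single curve cannot show the share with an unaided SBM.

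**Conclusion.** The gap is real and minor. Past the 24 h window, the plan is silent on rescue before the first SBM, and the planned curve mixes SBMs reached with and without it. Under the stated model, 65% to 28% of subjects at 1 to 3 SBM per week reach rescue-permitted time. At 25% daily uptake the two day-14 quantities differ by about 20 points at 2 per week (95.6 − 75.7) and 26 points at 1 per week (79.5 − 53.3). The gap depends on the assumed uptake, so it illustrates what the reader cannot see and does not estimate a bias. The direction of any bias is not established. At 2 per week or more, the median is unaffected when the three-day clock starts at the capsule.

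This is one descriptive secondary endpoint in an open-label, single-arm study, and no decision is attached to it.

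**What to change.** In section 17.8.5, keep the planned Kaplan-Meier curve and state that it counts the first SBM whether or not rescue came first. Add the cumulative incidence (Aalen-Johansen) of a first SBM without prior rescue, with the first rescue intake after the capsule as a competing event, and show the cumulative incidence of rescue before SBM beside it. Simple censoring at rescue is less suitable, because rescue is open only to subjects who have gone without an SBM and the censoring would be informative.

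While section 17.8.8 is open, correct a separate slip: subjects with no SBM by the end of observation are right censored, whereas the text says "subjects with no known SBM will be considered left censored".

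The cost is about two sentences and one more display, from rescue entries that the eDiary already collects. The rescue rule does not change. The drawback is that the reported proportion with an unaided SBM will be lower than the planned curve's figure if any subject takes rescue first and then has an SBM.

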17.8.6 Treatment by Center Interaction

Treatment by site interaction will be tested in the primary analysis at a significance level of 5%. Poolability across centers, for the primary end-point, will be assessed using logistic regression, baseline number of weekly SBM, and center will be entered into the models. Centers with less than 10 subjects will be grouped together by geographical area. If the center term is found significant, the reason for this will be further explored and rationalized. This evaluation may include demographic features, symptoms at presentation, clinical and treatment history, and site comparability in the features found to be associated with the primary efficacy variables.

